#### **4.6.3. Laboratory Safety Variables**

Hematology, chemistry, urinalysis, and pregnancy testing samples will be analyzed by a central laboratory.

Samples for laboratory testing will be collected according to visit schedule (Section 10.2). Tests will include:

##### **Serum Chemistry**

Sodium	Total protein, serum	Total bilirubin 
Potassium	Creatinine	Total cholesterol 
Chloride	Blood urea nitrogen (BUN)	Triglycerides
Carbon dioxide	Aspartate aminotransferase (AST)	Uric acid
Calcium	Alanine aminotransferase (ALT)	Creatine phosphokinase (CPK) 

Glucose	Alkaline phosphatase
Albumin	Lactate dehydrogenase (LDH)

 Direct and indirect bilirubin will be measured when the total bilirubin is above the ULN

 Low-density lipoprotein and high-density lipoprotein

 CPK isoenzymes will be measured when CPK >5 $\times$  the ULN

### **Hematology**

Hemoglobin	Differential:
Hematocrit	Neutrophils
Red blood cells (RBCs)	Lymphocytes
White blood cells (WBCs)	Monocytes
Red cell indices	Basophils
Platelet count	Eosinophils

### **Urinalysis**

Color	Glucose	RBC
Clarity	Blood	Hyaline and other casts
pH	Bilirubin	Bacteria
Specific gravity	Leukocyte esterase	Epithelial cells
Ketones	Nitrite	Crystals
Protein	WBC	Yeast

### **Other Laboratory Tests**

Serum and urine pregnancy testing will be performed for all female patients of childbearing potential at time points according to Section 10.2. The following tests will be performed at screening: HIV Ab, HBsAg, HBsAb, HBcAb, Hepatitis C antibody.

#### **4.6.4. Vital Signs**

The following vital signs parameters will be collected:

- Respiratory rate (bpm)
- Pulse (beats/min)

- Sitting systolic and diastolic blood pressures (mmHg)
- Body temperature (°C)

Vital signs will be collected predose at the time points according to Section 10.2.

#### **4.6.5. Body Weight and Height**

Body weight and height will be measured at time points according to Section 10.2.

#### **4.6.6. Physical Examination Variables**

The physical examination variable values are dichotomized to normal and abnormal. A thorough and complete physical examination will be performed at time points according to visit schedule (Section 10.2 ).

#### **4.6.7. 12-Lead Electrocardiography (ECG) Variables**

Standard 12-Lead ECG parameters include: Ventricular HR, PR interval, QRS interval, corrected QT interval (QTc Fridericia [ $QTcF = QT / [RR0.33]$ ] and QTc Bazett [ $QTcB = QT / [RR0.5]$ ]) ECG status: normal, abnormal not clinical significant or abnormal clinical significant. Electrocardiograms should be performed before blood is drawn during visits requiring blood draws. A standard 12-lead ECG will be performed at time points according to Section 10.2.

#### **4.6.8. Spirometry**

Spirometry will be performed in all subjects. If subjects have asthma and use short acting medications, the following instructions must be followed: after withholding the last dose of salbutamol/albuterol or levosalbutamol/levalbuterol for at least 6 hours, FEV1, forced vital capacity (FVC) and forced expiratory flow at 25% to 75% of forced vital capacity (FEF 25-75) will be determined at screening visit 2.

#### **4.6.9. Peak Expiratory Flow**

Peak expiratory flow will be measured using a peak flow meter (L/min) in any subject with a history of asthma prior to NAC at Screening Visit 2 and each NAC visit (Screening Visit 3 and Visit 16). Peak expiratory flow must be >80% predicted to perform the NAC in any subject with a history of asthma.

### **4.7. Pharmacokinetic (PK) Variables**

Serum samples for measuring functional dupilumab concentrations will be collected at time points according to Section 10.2. PK variables consist of functional dupilumab concentration and time (both actual and nominal).

### **4.8. Immunogenicity Variable**

The immunogenicity variables are ADA status, titer, neutralizing antibody (NAb) status, and time-point/visit. Serum samples for anti-dupilumab antibody will be collected at time points according to schedule (Section 10.2). Samples positive in the dupilumab ADA assay will be

further characterized for ADA titers and for the presence of neutralizing antibody (NAb) against dupilumab.

#### **4.9. Biomarkers Variables**

Biomarker samples will be collected at time points according to according to Section 10.2. Biomarker measurements (TARC, total IgE, Timothy Grass specific IgE, Timothy Grass specific IgG4, Timothy Grass specific IgG) will be performed in serum or plasma to determine effects on biomarkers of relevant physiological and pathogenic processes. Biomarker results will be used to better understand the pathophysiology of Timothy Grass allergy, mechanism of action of dupilumab and possible toxicities.

## 5. STATISTICAL METHODS

For continuous variables, descriptive statistics will include the following: the number of patients reflected in the calculation (n), mean, standard deviation, median, first quartile (Q1), third quartile (Q3), minimum, and maximum.

For categorical or ordinal data, frequencies and percentages will be displayed for each category.

All data will be summarized by the following 4 treatment groups defined in Section 1.1.

### 5.1. Demographics and Baseline Characteristics

Demographics and baseline characteristics will be summarized by treatment group for FAS. Listing of demographics and baseline characteristics will be presented.

### 5.2. Medical History

Medical history will be summarized by primary SOC and PT for each treatment group. The table will be sorted by decreasing frequency of SOC followed by PT based on the overall incidence across treatment groups. Medical history will be listed.

### 5.3. Prior/Concomitant Medications/Procedures

Number and proportion of patients taking prior/concomitant medications, prohibited medications and rescue medications will be summarized, sorted by decreasing frequency of ATC Level 2 and ATC level 4, based on the overall incidence for the combined treatment groups. Patients will be counted only once for each medication class (ATC level 2 and 4) linked to the medication.

Number and proportion of patients taking prior/concomitant procedures will be summarized, sorted by decreasing frequency of SOC and PT based on the overall incidence for the combined treatment groups. Patients will be counted only once for each SOC and PT linked to the procedure.

Concomitant medications used to treat SCIT related adverse events will be tabulated separately.

Prior medications or procedures started before screening visit and started between screening visit and first injection date will be summarized separately.

Listing of medications and procedures will be provided.

### 5.4. Rescue/ Prohibited Medications

Number and proportion of patients taking prohibited procedures and rescue procedures will be summarized, sorted by decreasing frequency of SOC and PT based on the overall incidence for the combined treatment groups. Patients will be counted only once for each SOC and PT linked to the procedure.

Concomitant treatments for allergies including allowed and rescue treatments (i.e., both medications and procedures) will be analyzed similarly.

## 5.5. Subject Disposition

The following summaries by table will be provided:

- The total number of screened patients
- The total number of randomized patients: received a randomization number
- The total number of patients in each analysis set
- The total number of patients who completed the study and discontinued the study with the reason of discontinuation
- The total number of patients who completed the study treatment and discontinued the study treatment with the reason of discontinuation

The following listings will be provided:

- Listing of patient disposition including: date of randomization, date of the last visit, received dose, completed study drug or discontinued by reason, completed study or discontinued by reason
- A listing of patients randomized but not treated, and patients randomized but not treated as randomized
- A listing of patients prematurely discontinued from the study or treatment, along with reasons for discontinuation
- Summary table with listing of protocol deviations will be provided

Time to the discontinuation will be assessed by Kaplan-Meier estimates (K-M plot) for each treatment group.

## 5.6. Extent of Study Treatment Exposure and Compliance

### 5.6.1. Measurement of Compliance

The compliance with study treatment will be calculated separately for dupilumab injection and SCIT injection as follows:

Treatment Compliance = (Number of study drug injections during exposure period) / (Number of planned study drug injections during exposure period) x 100%, where the study drug injections can be dupilumab (or placebo dupilumab) injection, or SCIT (or placebo SCIT) injection.

For treatment compliance calculation of dupilumab injection, the two injections taken at the randomization visit 4 will be counted as 1 injection.

For treatment compliance calculation of SCIT injection, all the injections taken at the same visit will be counted as one single injection. Because due to the judgement of investigators to avoid patients having intolerable allergic symptoms, patients may not receive all the planned SCIT injections for a visit according to protocol.

Summary of study drug administration will include the number of study drug doses administered and treatment compliance. The treatment compliance will be presented by the following specific ranges for each treatment group: <80%, and  $\geq$ 80%.

Listing of dose administration: including date/time, study day, number of injections, locations of injections, dosing information, and whether or not the total dose is administered for each dose will be presented.

### **5.6.2. Exposure to Investigational Product**

The duration of treatment exposure during the study in day is calculated as:

$$(\text{Date of last study drug injection} - \text{date of first study drug injection}) + 14 \text{ days}$$

The calculations are regardless of temporary dosing interruption. The duration of exposure during the study will be summarized by treatment group using number of patients, means, SD, minimums, medians, and maximums.

In addition, the duration of exposure will be summarized categorically by counts and percentages for each of the following categories and cumulatively by these categories as well:

$\geq 14$  days,  $\geq 28$  days,  $\geq 42$  days,  $\geq 56$  days,  $\geq 70$  days,  $\geq 84$  days,  $\geq 98$  days,  $\geq 112$  days and  $\geq 126$  days.

The duration of observation period during the study in day is calculated as:

$$(\text{Date of the last visit} - \text{date of the first study drug injection}) + 1 \text{ day.}$$

The number (%) of patients with observation periods will be presented by specific time periods. The time periods of interest are specified as:  $< 8$  days,  $\geq 8$  days,  $\geq 15$  days,  $\geq 22$  days,  $\geq 29$  days,  $\geq 36$  days,  $\geq 43$  days,  $\geq 50$  days,  $\geq 57$  days,  $\geq 71$  days,  $\geq 92$  days,  $\geq 113$  days,  $\geq 120$  days,  $\geq 141$  days, and  $\geq 169$  days.

## **5.7. Analyses of Efficacy Variables**

For all efficacy variables, unless specified, the analysis will be comparisons of

- dupilumab + SCIT versus SCIT
- dupilumab versus placebo
- dupilumab + SCIT versus dupilumab for percent change and change in TNSS AUC only

The efficacy analyses will be based on the FAS Population. All statistical tests will be 2-sided at the 5% significance level. All confidence intervals (CIs) will be 2-sided 95% CIs.

### **5.7.1. Analysis of Primary Efficacy Variable**

The primary endpoint will be analyzed by using the analysis of covariance (ANCOVA) model as the primary analysis method. The model will include treatment group being the main factor and baseline value as the covariate. The missing AUC value at a visit directly when a patient does not have any TNSS score collected at the visit, will be imputed by multiple imputation (MI) methods 40 times to generate 40 complete data sets by using the Statistical Analysis System (SAS) procedure MI following the 2 steps below:

Step 1: The monotone missing pattern is induced by Markov Chain Monte Carlo (MCMC) method in MI procedure using seed number 16115. The monotone missing pattern means that if a patient has missing value for a variable at a visit, then the values at all subsequent visits for the same variable are all missing for the patient.

Step 2: The missing data at subsequent visits will be imputed using the regression method for the monotone pattern with seed number 51161 and adjustment for covariates including treatment groups and relevant baseline.

Each of the 40 complete datasets will be analyzed using an ANCOVA model with treatment group being the main factor and baseline value as the covariate. The SAS MIANALYZE procedure will then be used to generate valid statistical inferences by combining results from the 40 analyses using Rubin's formula. The least-squares (LS) mean for each treatment group with its corresponding standard error (SE), the LS mean difference between treatment group and its corresponding SE and 95% CI, and the p-value corresponding to the between-treatment-group difference will be reported.

In case of missing TNSS scores at one or more time points at a visit, all available TNSS scores collected at the visit will be used to calculate the AUC at the visit. The missing TNSS score at timepoints will not be imputed. The algorithm for calculation of AUC is provided in Section [6.2](#).

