##### 10.4.3. Efficacy Analyses

###### 10.4.3.1. Primary Efficacy Analysis

The primary endpoint will be analyzed by using the multiple imputation (MI) with analysis of covariance (ANCOVA) model. Missing data will be imputed 40 times to generate 40 complete data sets by using the Statistical Analysis System (SAS) procedure MI. Each of the 40 complete datasets will be analyzed using an ANCOVA model with treatment group being the main factor and baseline value as the covariate. The SAS MIANALYZE procedure will then be used to generate valid statistical inferences by combining results from the 40 analyses using Rubin's formula.

All observed data will be used for analysis. Sensitivity analysis such as ANCOVA model with last observation carry forward (LOCF) method will also be conducted. Additional details on sensitivity analyses will be provided in the SAP.

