### 2.2. Sample Size and Power Considerations

[figure not shown]
Approximately 100 patients are planned to be randomized. It is estimated that with 25 subjects per group, the study will have 80% power to detect a difference of 29% between dupilumab plus SCIT and placebo plus SCIT with respect to percent change from baseline in TNSS AUC (0-1h) at week 17, assuming that the mean percent changes from baseline values are -55% and -26% for dupilumab plus SCIT and placebo plus SCIT, respectively, and a common standard deviation (SD) of 35%. The significance level is set to 2-sided, 0.05 level.

The assumptions used for primary endpoint were based on the study result from the Scadding (2017) study. The Scadding study shows after 1-year treatment, the difference between SCIT and placebo is 34% for the percent change in TNSS AUC (0-1h) at 1 year. A similar magnitude of improvement by adding dupilumab onto SCIT is assumed for the sample size calculation.

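### SAP 5.7.1 pools 40 ANCOVAs by Rubin's formula without giving the complete-data degrees of freedom, so a literal application is slightly anti-conservative at 25 per arm

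*SAP*

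**What the plan says.** SAP 5.7.1 sets out the primary analysis in some detail: 40 imputations, an MCMC step and a regression step each with its seed, and an ANCOVA on treatment group and baseline in every completed data set. MIANALYZE is then "used to generate valid statistical inferences by combining results from the 40 analyses" by Rubin's formula, and a least-squares mean difference, standard error, 95% interval and p-value are reported. Protocol 10.4.3.1 has the same step: the procedure "will then be used to generate valid statistical inferences by combining results from the 40 analyses".

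SAP 5.7 fixes the error rates: "All statistical tests will be 2-sided at the 5% significance level" and "All confidence intervals (CIs) will be 2-sided 95% CIs". SAP 2.2 gives the size: "It is estimated that with 25 subjects per group, the study will have 80% power".

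Neither document gives the complete-data df, mentions a small-sample adjustment, or says whether the ANCOVA contains the two arms being compared or all four. SAP 5.7.2 carries the primary approach over to the continuous secondary and exploratory endpoints unless otherwise specified. The biomarker endpoints are outside this point, because they use a rank-based ANCOVA with LOCF.

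**The concern.** Rubin's classical df measure only the uncertainty from using a finite number of imputations. They take the complete-data analysis to be a large-sample one. That is harmless in a large trial, but here each comparison rests on 25 subjects per arm. Raising the number of imputations to 40 pushes the classical df up further, so the pooled test can claim more df than the ANCOVA would have with no data missing. The Barnard-Rubin adjustment prevents this, but it needs the complete-data df as an input, and the plan does not supply it.

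What is at stake is whether the reported p-value and interval match the stated 5% and 95%. There is also a question of consistency. SAP 5.7.1 plans a sensitivity ANCOVA on observed data, which uses ordinary residual df. Near the 5% boundary the primary and sensitivity results could disagree only because they use different reference distributions.

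**Working it through.** **Inputs.** 25 per group, SD 35, difference 29 points, two-sided 0.05 (SAP 2.2); four arms, 1:1:1:1 (SAP 2.1); m = 40 and ANCOVA on treatment and baseline (SAP 5.7.1). No missing rate is stated, so the share of the pooled variance due to missing data, λ, is assumed to lie between 0 and 20%.

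**The plan's own figure.** SAP 2.2 says "the study will have 80% power to detect a difference of 29" points. A two-sample t test with 48 df gives 81.9% power at 25 per group, and 24 per group is the smallest size that reaches 80%. The sample size is therefore in order.

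**Complete-data residual df, ν₀.**
- Two arms: 50 − 3 = 47, t critical value 2.012.
- Four arms: 100 − 5 = 95, t critical value 1.985.

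**Classical Rubin df.** ν_R = (m − 1)(1 + 1/r)², where r is the relative increase in variance from missing data. This equals (m − 1)/λ² with λ = r/(1 + r). At λ = 0.20, 39/0.04 = 975. At λ = 0.10, 39/0.01 = 3,900. With nothing missing, r = 0 and ν_R is infinite.

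**Barnard-Rubin df.** ν_obs = [(ν₀ + 1)/(ν₀ + 3)] ν₀ (1 − λ), and ν_BR = 1/(1/ν_R + 1/ν_obs). For example, with two arms and λ = 0.10, ν_obs = (48/50) × 47 × 0.9 = 40.6 and ν_BR = 40.2.

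In the table, size is the two-sided tail area beyond the classical critical value under a t distribution with ν_BR df. Narrowing is one minus the ratio of the two critical values.

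| Model | λ | Classical df (critical value) | Barnard-Rubin df (critical value) | CI too narrow by | Size |
|---|---|---|---|---|---|
| Two arms | 0 | infinite (1.960) | 47 (2.012)* | 2.6% | 5.6% |
| Two arms | 2% | 97,500 (1.960) | 44.2 (2.015) | 2.7% | 5.6% |
| Two arms | 10% | 3,900 (1.961) | 40.2 (2.021) | 3.0% | 5.7% |
| Two arms | 20% | 975 (1.962) | 34.8 (2.031) | 3.4% | 5.8% |
| Four arms | 0 | infinite (1.960) | 95 (1.985)* | 1.3% | 5.3% |
| Four arms | 2% | 97,500 (1.960) | 91.1 (1.986) | 1.3% | 5.3% |
| Four arms | 10% | 3,900 (1.961) | 82.0 (1.989) | 1.5% | 5.3% |
| Four arms | 20% | 975 (1.962) | 69.2 (1.995) | 1.6% | 5.4% |

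*With nothing missing, the exact comparison is with the ANCOVA's own residual df.

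**Simulation check.** The imputation, ANCOVA and pooling were simulated under the null hypothesis, with 8,000 trials per setting and 5%, 10% or 20% of values missing at random positions. With classical df, rejection was 5.5% to 6.1% (two arms) and 5.2% to 5.5% (four arms). With Barnard-Rubin df it was 4.8% to 5.4% and 4.9% to 5.2%. The Monte Carlo standard error is about 0.25 points. Within each setting the classical rate was higher by 0.6 to 0.7 points (two arms) or 0.3 to 0.4 points (four arms).

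**In trial units.** The planning standard error is 35 × √(2/25) = 9.90 points, before any gain from baseline adjustment. With nothing missing, the half-width is 19.40 points at 1.960, against 19.92 with 47 df or 19.65 with 95 df. A statistic of 1.97 would be reported as p = 0.049, where the t test gives 0.055 (47 df) or 0.052 (95 df).

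**The case against.** A reader might infer that the plan prescribes normal critical values, or that the reported interval is bound to be too narrow. The documents support neither. They never mention a normal reference, and Rubin's formula refers the pooled estimate to a t distribution. That distribution is merely close to normal here because its df are so large. Nor does the SAP exclude supplying the complete-data df. It describes a method rather than program code, and a programmer may well set the option. The anti-conservative result follows from applying the text literally; it is not an established fact about the analysis that will be run.

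The effect is also small. The SAP does not favour the two-arm model, and with four arms the excess is only 0.3 to 0.4 points. This is a phase 2a study without multiplicity control, so the shift in secondary and exploratory p-values changes no stated decision rule. For the primary endpoint, only a statistic in the narrow band between about 1.96 and 2.03 would change sides. If nothing were missing, the observed-data ANCOVA would show the correct t-based result alongside.

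All of this stands, and it limits the point to a minor one. It does not remove it. The SAP fixes the imputation number and both seeds but leaves open a setting that can change the primary p-value. The rule it does name, taken alone, does not deliver the stated 5% and 95%.

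**Conclusion.** The point holds as a minor one. Pooling by Rubin's formula alone gives a near-normal critical value of 1.960 to 1.962 where the ANCOVA has 47 or 95 residual df. The nominal 5% test would then run at about 5.6% to 5.8% in a two-arm model or 5.3% to 5.4% in a four-arm model. The 95% interval would be about 2.6% to 3.4% or 1.3% to 1.6% too narrow.

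These figures assume 25 analysed per arm, missing information of at most 20%, and no small-sample df in the pooling step. At an extreme 40% missing information they would be about 6.0% and 4.5% (two arms) or 5.5% and 2.2% (four arms). The design, the sample size and the choice of multiple imputation are not in question.

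**What to change.** Add two statements to SAP 5.7.1:

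1. Say whether the ANCOVA contains the two arms being compared or all four, since this sets the complete-data residual df (47 or 95 at the planned size).
2. Say that MIANALYZE will be run with EDF= the complete-data ANCOVA residual df, so that p-values and intervals use the Barnard-Rubin df, and that this applies to every endpoint analysed by multiple imputation with ANCOVA.

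The cost is a short SAP addition before database lock and one procedure option. Intervals become roughly 1% to 3% wider (at the top of the assumed range, 2.031/1.962 = 1.035). No change to data collection, design or sample size is needed.

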### **Sensitivity analyses:**

- Post-baseline Last Observation Carried Forward (LOCF) approach will be used to impute the primary efficacy data at week 17, then the imputed data will be analyzed using ANCOVA model.
- All observed data without imputation will be included for analysis using ANCOVA model.

The primary efficacy analyses will be performed on FAS, as well as on PPS as a supportive analysis.

### **Subgroup analysis:**

Subgroup analysis for the primary endpoint based on FAS will be performed. Descriptive statistics will be displayed for each subgroup for each treatment group.

